The study uses a wait-list **experimental design** to estimate treatment impacts, with 30 Ohio classrooms assigned to the treatment condition and 20 to the control condition. All remaining 40 classrooms will be recruited by our partners at external sites and serve control condition classrooms. Within each classroom, the focal participants are 30 children with LI, one selected per classroom using a priori exclusionary and inclusionary criteria. The wait-list design allows eligible children with LI in control classrooms to receive treatment in the spring semester; this also allows for ongoing evaluation of changes in socialization processes in treatment classrooms through spring. Study methods with OSU classrooms use a sequential cohort design, with 15 classrooms participating in each of two consecutive years to disperse study activities over a 24-month period. Classrooms will be recruited via our extensive network of affiliated preschool programs across the state of Ohio, with eligible classrooms utilizing a 50/50 inclusive service delivery model (50% of children with disabilities). In the fall of each year, once all 15 classrooms are recruited, simple random assignment will be used to allocate 10 classrooms to the treatment group and 5 to the control group, with the latter implementing intervention in spring per the wait-list design. In addition, our colleagues at the University of Kansas, are employing similar observation methods. We will thus incorporate 20 classrooms (University of Kansas) to serve as control condition classrooms, allowing for a more robust sample of natural conditions in preschool classrooms across contexts.

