### **b. Sample**

This study examines the socialization experiences of preschool children with LI inclusive classrooms and the entire classroom social network. Thus, we seek to consent all children in each classroom as participants in this study. For children who are not focal children or peers assisting with the intervention, we will seek caregiver consent to observe their children in the classroom and for caregivers to complete a simple questionnaire about their children. We typically are able to actively or passively consent 90% of children in a classroom.

Focal children (n = 30). We describe inclusionary and exclusionary criteria for the 30 focal children with LI. First, we identify all children's positions (n = 495) within the classroom social network using a teacher matrix conducted in fall of the academic year; from this network we calculate a child-level social network index (i.e., individual degree centrality; lower scores are characteristic of social exclusion (Justice, Chen, et al., 2019)). Second, teachers simultaneously complete the Developmental Pragmatic Profile (DPP) (Wiig, Secord, & Semel, 2004) for each child in the classroom. This is a 26-item psychometrically sound checklist assessing children's pragmatic skills (e.g., conversational abilities, giving information), and DPP scores have strong classification accuracy in differentiating children with LI from non-affected classmates (Justice, Ahn, & Logan, 2019). Third, teachers also use a checklist to identify children with LI in each classroom per four criteria: the child (1) is on the caseload of a speech-language pathologist, (2) has no known additional diagnoses causal of LI, such as ASD, (3) primarily communicates in English, and (4) is greater or equal than 42 months of age. Finally, among the children with LI, we select the target child based on the lowest centrality scored weighted by DPP score, so that focal children represent the most socially isolated children with the poorest social-pragmatic communication skills.

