Main Study: Focal children in OSU-based treatment condition classrooms will receive peer-mediated PRT per procedures detailed by Brock et al (Brock, Dueker, & Barczak, 2018). PRT procedures are facilitated by a classroom facilitator—a classroom teacher or teaching assistant—who will receive ongoing training and support from research staff. Focal children receive peer-mediated pivotal response treatment. With carefully identified classroom peers, facilitators hold four 15-minute training sessions with the peer group, each developing 1 of 4 strategies to use to engage with the target child. The facilitator explicitly identifies the focal child ('buddy') and asks the children to use four strategies to play with the child during center time: a) offer your buddy some play options; b) show and talk about how to play with your buddy; c) compliment your buddy; and d) show your buddy how to take turns. After the trainings are complete, the facilitator provides ongoing support to peers during center time to implement the strategies by regularly encouraging them and supporting them to use the strategies, praising them when they use the strategies well, and reviewing their interactions with the focal child at the end of center time. Facilitators provide this support during center time at least 3 times weekly for a 12-week period.

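### Assignment is triggered by classroom recruitment and nothing requires the focal child to be fixed first, so teachers who know their arm may supply the ratings that select that child

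*Combined protocol and SAP*

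**What the plan says.** Section III.a (Research Design) describes two yearly cohorts of 15 Ohio classrooms. In the fall, "once all 15 classrooms are recruited, simple random assignment will be used to allocate 10 classrooms to the treatment group". The other five classrooms are wait-list controls and start the intervention in spring. Recruitment is the only condition attached to assignment. The same section says there is one focal child per classroom, "one selected per classroom using a priori exclusionary and inclusionary criteria".

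Section III.b (Sample) describes how that child is found. Centrality is calculated "using a teacher matrix conducted in fall of the academic year". Teachers rate every child on the DPP at the same time. Then "teachers also use a checklist to identify children with LI in each classroom per four criteria"; this step has no date of its own. Finally, "we select the target child based on the lowest centrality scored weighted by DPP score".

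Section III.c (Intervention Implementation) says who delivers the treatment: "PRT procedures are facilitated by a classroom facilitator—a classroom teacher or teaching assistant—who will receive ongoing training and support from research staff".

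Section III.d (Measures and Instrumentation) states blinding for researcher observers, and for the double-coding of focal-child observations. It states none for teachers. It also lists the teacher DPP as a language outcome, rated in fall, winter and spring for focal children.

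**The concern.** Classrooms are randomised, but many of the analyses concern one child per classroom, chosen from the teacher's own ratings. Randomising classrooms makes those children comparable only if the choice cannot depend on arm. If ratings are made after the teacher learns the arm, it can. A teacher who is about to deliver the intervention might, without intending to, rate children differently from a teacher who will not start until spring. This is identification bias, familiar from cluster-randomised trials.

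What is at stake is the randomised Ohio comparison for the Aim 1 peer interaction, play and talk outcomes and for the Aim 2 skill outcomes. There is a second route to bias. If the DPP used for selection is also the fall baseline, an arm-aware low rating would both help to select the child and enlarge the apparent later gain. Extra repeated measurements would not reduce either bias.

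**Working it through.** The plan gives no figure on this point, so there is none to reproduce. The check has two parts.

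**Order of the steps, section against section**

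- Assignment (III.a): fall, once the cohort's 15 classrooms are recruited.
- Selection ratings (III.b): matrix in fall, DPP at the same time, checklist undated. No order relative to assignment is given.
- Raters (III.b): teachers, for both scores that rank the children and for the checklist that defines the candidates.
- Delivery (III.c): a classroom teacher or teaching assistant, so the classroom's staff must learn the arm.
- Blinding (III.d): observers only.

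Two sequences fit this text. In one, ratings are completed, the child is fixed and assignment follows. In the other, assignment is made and disclosed and ratings follow. Under the first, the choice of child cannot depend on arm; under the second it can. I found no sentence that excludes the second. The a priori criteria fix the rule, but not when its inputs are rated or whether the rater knows the arm.

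**Illustration of size, on assumed inputs**

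Assumptions:

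- There are k = 3, 4 or 5 eligible children per classroom. Section III.a requires at least 3 children with LI, but gives no upper limit and does not say how many would pass the checklist.
- True status scores are independent standard normal.
- In a share f = 0.10 to 0.30 of classrooms in one arm, and none in the other, the second-lowest child is chosen instead of the lowest.

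The expected gap is g(k) = E[second lowest] − E[lowest], from 1,000,000 simulated draws:

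- k = 3: 0.00 − (−0.85) = 0.85 SD
- k = 4: −0.30 − (−1.03) = 0.73 SD
- k = 5: −0.49 − (−1.16) = 0.67 SD

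The imbalance between arms is f × g(k):

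- Smallest: 0.10 × 0.668 = 0.067, about 0.07 SD
- Largest: 0.30 × 0.8465 = 0.254, about 0.25 SD

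This is a shift in true status. It would not show in the recorded selection score, because a child chosen through distorted ratings has the lowest recorded score by construction.

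For scale, 10 and 5 classrooms a year for two years give 20 against 10. With one focal child each, an assumed two-sided alpha of 0.05 and 80% power, and no covariates or repeated measures, the detectable difference is (1.960 + 0.842) × √(1/20 + 1/10) = 2.802 × 0.3873 = 1.085, about 1.09 SD. Section III.a also gives 30 and 20 Ohio classrooms, which does not agree with 20 and 10. I used the figures attached to the randomisation step.

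**The case against.** The strongest replies, and what remains of each:

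- **The order is unstated, not wrong.** Recruitment of 15 classrooms sets an earliest time for assignment; the team may well rate first. This stands. A reader might infer that the plan places assignment before selection, but both steps are dated only to fall. The defect is that the wrong order is permitted.
- **Wait-list teachers also deliver the intervention, in spring.** They may have much the same motive to favour a child who is easier to work with. This stands too: only a difference between arms causes imbalance, and the documents do not show that there would be one.
- **The research team selects, by a fixed rule.** To steer the choice knowingly, a teacher would have to distort a class matrix or 26-item ratings and foresee how they combine. Speech-language caseload, age and main language are largely factual. This makes deliberate steering less likely. It does not protect against unintended shifts in the two ranking scores, both of which are teacher judgements.
- **Observers are blind and the models adjust for covariates.** Blind observation protects outcome measurement, not the choice of whom to observe. Section III.g (Data Analysis) promises only relevant covariates, and adjusting for a rating that was itself made with knowledge of the arm need not remove the imbalance.
- **The illustrated bias is small beside 1.09 SD.** That is so. But a detectable difference describes random error, whereas this would be a systematic error.

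A reader might also infer that families consent knowing their arm. Section III.b says only that consent is sought, and the consent pages are not in the text reviewed, so that reading is unsupported.

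**Conclusion.** The concern holds in a limited form. As written, assignment may come before the teacher ratings that select the focal child, and nothing keeps teachers unaware of arm until selection is complete. If arm-aware rating differs between immediate-treatment and wait-list teachers, focal children in the randomised Ohio classrooms would not be comparable. The possible reuse of the selection DPP as an outcome baseline adds to the exposure.

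The size is unknown. The range of 0.07 to 0.25 SD should not be read as an estimate of bias: the number of candidates, the normal scores, the affected share and the restriction to one arm are all assumptions. Nor do the documents show that any teacher would rate differently. The case for acting is that the safeguard is cheap and the bias, if present, could not reliably be removed in analysis.

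**What to change.** Change the trigger in section III.a. Each fall, the teacher matrix, DPP and LI checklist are completed in all 15 classrooms, and the focal-child ID is computed and locked in each. Only then is the assignment generated and released.

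If a cohort has already been assigned, report the order actually followed and compare focal children's baseline centrality and DPP by arm. Because recorded teacher ratings can hide a shift in true status, include centrality from researcher observation where an observation predates the intervention.

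The change needs no new data or staff. Its cost is time: every classroom waits for the slowest of the 15. The team should check that four training sessions and the 12-week support period in treatment classrooms still fit before the wait-list classrooms begin in spring. The change protects only the randomised Ohio comparison. External-site classrooms are controls by design, so the order of steps makes no difference there.

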### **Descriptives and possible covariates**

Pilot: Teachers: Teachers will complete a survey prior to the pilot and provide demographics. The survey will also include the peer matrix and 5 questions about past social supports and experience with peer-mediated interventions. During week 6 of the pilot, teachers will complete an 8 item questionnaire to provide information on the feasibility and tolerance of implementing the pilot intervention in their classrooms; Parents: will complete an IFQ with their consent form to determine eligibility. Caregivers of peers and target children will be asked to complete one survey during the pilot, which will collect the following information: demographics, household socioeconomic status (caregiver education levels), a set of 5 items to capture child social network information; the DPP. Only focal child and peer parents who will complete the survey during the pilot.

Peer and target children will be asked to complete a brief 4 minute interview during weeks 1 and 6 of the pilot.

Main Study: Descriptives and potential covariates to be captured and explored in analyses include (1) classmates' language skills (fall and spring DPP completed for each child by teacher), (2) classroom composition characteristics including percentage of children with disabilities, gender, and age (provided by teachers in fall), and (3) focal child sociodemographic factors. For the latter, we collect a questionnaire from the primary caregiver in the fall and spring (in accordance with the approved/signed informed consent materials) to assess household socioeconomic status (caregiver education levels and employment status, household composition, and transience—including whether or not the family experienced a serious family event over the last school year to be answered in spring), home literacy activities per established protocols (Justice, Logan, Işitan, & Saçkes, 2016), and child language history.

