#### **g. Data Analysis**

Aim 1 investigates the effects of peer-mediated PRT on the peer interactions and social status (indicated by individual centrality) within the classroom social network for children with LI. We assess this aim based on 6 to 24 repeated measurements for each outcome variable using multilevel growth models (Raudenbush & Bryk, 2002) to investigate changes in key outcomes over the school year and to accommodate the wait-list experimental design. Longitudinal measurements will be nested within participants and predicted by the time of measurement as well as time-specific intervention status. We include interaction terms between time of measurement and intervention status so that any accelerating or decelerating effects of intervention can be captured. In all models, we control for relevant covariates to increase precision of parameter estimates and power (Hox, Moerbeek, & Van de Schoot, 2010; Raudenbush, Martinez, & Spybrook, 2007). To assess treatment effects on peer interactions, we use the number of peer interaction, number of appropriate peer play, and duration of peer talk for the focal children as the outcome variables in the growth models. Depending on the distribution of the variables, appropriate linear or generalized linear models (e.g., Poisson) will be fitted. To examine treatment effects on social status, we compare the trajectories of individual centrality for the focal children and their classmates, controlling for classroom-level variation. Specifically, intervention effects are tested on key components of the trajectories, such as intercept, linear slope and quadratic slope (i.e., the slowing or acceleration of growth). The growth curves for different groups (treatment, wait-list control, and peer) can then be estimated. Aim 2 determines the extent to which peer-mediated PRT contributes to focal children's social, behavioral, and linguistic skills via the mediation of improved socialization experiences. For this aim, we employ multivariate latent growth models, where latent growth curves of socialization indices and child skills can be modelled simultaneously and the relationships between latent growth parameters examined. In particular, two latent slopes (fall and spring) will be specified for the socialization growth curve to capture the differential growth rate with and without intervention; intervention status will be used as a predictor of the two socialization slopes. Due to the sample size limitation, we will examine one socialization index and one skill variable at a time. We will focus on the following pathways: (a) effect of intervention on focal children's socialization experiences at fall, winter, and spring; and (b) effects of socialization experiences on child skills at fall, winter, and spring. Paths (a)\*(b) allow us to test the indirect effects of PRT on social, behavioral, and linguistic skills. To estimate the mediation effect, we use the product-of-coefficient approach (MacKinnon, Lockwood, Hoffman, West, & Sheets, 2002) with a bootstrapping procedure (Preacher & Hayes, 2004, 2008). This method does not require the assumption of normality for the sampling distribution of the product-of-coefficient. Finally, Aim 3 examines changes in classroom social network dynamics over the school year, and tests the effects of peer-mediated PRT on peer socialization at the classroom level. To address this aim,

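### Simple random assignment of 15 classrooms a year is valid but leaves avoidable chance imbalance; covariate-constrained assignment would be a cheap improvement with a modest gain in precision

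*Combined protocol and SAP*

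**What the plan says.** Under Research Design, the Ohio arm runs as yearly cohorts, with "15 classrooms participating in each of two consecutive years". When a year's 15 classrooms have all been recruited, "simple random assignment will be used to allocate 10 classrooms to the treatment group and 5 to the control group". No stratification, matching or other restriction is described beyond that fixed split. The smaller group starts the intervention in spring.

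The same section gives another count, "30 Ohio classrooms assigned to the treatment condition and 20 to the control condition", and adds classrooms that are not randomised: "All remaining 40 classrooms will be recruited by our partners at external sites and serve control condition classrooms". A later sentence there mentions 20 control classrooms from one partner university.

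Under Sample, one focal child per classroom is chosen from social-network centrality, "using a teacher matrix conducted in fall of the academic year", weighted by the teacher-rated DPP score. Under Descriptives and possible covariates, classroom composition is also a fall measure. The order of these ratings and the random assignment is not stated.

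Under Data Analysis, Aim 1 says that in all models "we control for relevant covariates to increase precision of parameter estimates and power". The covariates are not named there.

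**The concern.** The randomised comparison rests on about 30 classrooms with one focal child each. Unrestricted assignment of so few units often leaves the arms visibly different on characteristics related to the outcome. Centrality is itself an Aim 1 outcome and DPP a language outcome, so their starting values are likely to be prognostic.

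The batch of 15 is complete before assignment, and the ratings are planned for the same fall. Balance could therefore be secured in the draw. Left to later adjustment, chance imbalance makes the covariates partly collinear with treatment, which widens the standard error of the effect. It also leaves the result more dependent on which covariates are chosen, and the plan does not name them.

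**Working it through.** The documents give no power calculation, SD, effect size or balance target, so there is no planned figure to reproduce.

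**Inputs.** From Research Design: 10:5 per year and two years, so 2 × 10 = 20 against 2 × 5 = 10. This agrees with the 30 focal children under Sample. The alternative count in the same section is 30:20. Assumptions: independent, normally distributed classroom-level covariates; two to four of them; 0.5 SD as the threshold for a material gap.

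**Chance of imbalance.** The standardised difference between arms is approximately normal with SD √(1/n₁ + 1/n₂). For one covariate, P(|d| > 0.5) = 2[1 − Φ(0.5/SD)]. For at least one of k, it is 1 − (1 − p)^k.

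| Count | SD | One covariate | Any of three | Any of four |
|---|---|---|---|---|
| 20:10 | √(1/20 + 1/10) = 0.387 | 20% | 48% | 58% |
| 30:20 | √(1/30 + 1/20) = 0.289 | 8% | 23% | 29% |

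Simulation of two cohorts of 15 agrees for 20:10 (about 48% and 58%). If the covariates are correlated at 0.5 (assumption), the figures fall to about 42% for three and 50% for four.

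**Effect of constraining the draw.** Each cohort has C(15,5) = 3,003 possible allocations. Drawing at random from the best-balanced 10% (about 300) reduces the chance of any gap above 0.5 SD to essentially zero for three covariates and under 1% for four.

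**Precision after adjustment.** The table shows the mean variance of the treatment coefficient, adjusted for cohort and the k covariates, relative to perfect balance (4,000 simulated trials per row, two-group comparison).

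| k | Simple | Constrained | Ratio | Standard error |
|---|---|---|---|---|
| 2 | 1.085 | 1.004 | 0.925 | −4% |
| 3 | 1.131 | 1.015 | 0.897 | −5% |
| 4 | 1.185 | 1.031 | 0.871 | −7% |

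The gain is therefore about 7-13% of the variance, since √0.925 = 0.96 and √0.871 = 0.93.

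**From covariate gap to outcome gap.** Suppose three or four equally strong, independent covariates explain 20-40% of the outcome variance (assumption). A 0.5 SD gap in one covariate then moves the outcome by 0.5 × √(R²/k). This runs from 0.5 × √(0.2/4) = 0.11 SD to 0.5 × √(0.4/3) = 0.18 SD. The chance that all of them together produce a 0.5 SD outcome gap is 2[1 − Φ(0.5/(√R² × 0.387))], which is 0.4% at R² = 0.2 and 4% at R² = 0.4.

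**The case against.** The strongest reply is that nothing is broken. Simple assignment with fixed yearly counts is unbiased, balances cohort exactly, and is followed by covariate adjustment in every model. That stands, and it limits this point to efficiency and robustness.

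A reader might infer that a half-SD baseline gap rivals a plausible treatment effect. The documents do not support that: the gap is in a covariate, and on the assumptions above it moves the outcome by only 0.11-0.18 SD. A reader might also quote the larger variance saving without adjustment, about 11-36% when the covariates explain 20-40% of the outcome. That describes an analysis the plan does not propose.

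Three further limits stand:
- The planned growth models use repeated measurements and time-specific intervention status, with wait-list classrooms crossing over in spring. The two-group calculation does not represent this.
- The rule that eligible classrooms follow a 50/50 inclusive model restricts variation in the percentage with disabilities, so balancing on it adds little.
- Aim 2 is already confined to one socialization index and one skill at a time because of sample size, so extra covariates are not costless there.

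Feasibility is a fair challenge, because the plan does not say that ratings precede assignment. It is only partly an obstacle. The matrix and DPP must be completed in fall to select the focal child before treatment can start, so the added delay is the wait for the slowest of the 15 classrooms.

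**Conclusion.** The point holds as a cheap improvement, not as a flaw that invalidates the trial. On the 20:10 count with independent covariates, a gap above 0.5 SD has a 20% chance for any one covariate and about a 50% chance for at least one of three. The 30:20 count gives 8% and 23%. The two counts cannot both describe the randomised comparison and must be reconciled.

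Given the planned adjustment, constraining the draw is worth about 7-13% of the variance, or a 4-7% smaller standard error, for two to four balancing variables. That is for a simple two-group comparison at 20:10; the gain in the full growth model was not calculated and may differ. With no power target in the documents, it cannot be expressed as power gained. The external control classrooms are a separate source of imbalance that this change does not touch.

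**What to change.** 1. State in Research Design that the fall teacher matrix, the DPP and focal-child selection are complete for all 15 classrooms of a cohort before assignment.
2. Replace simple assignment with covariate-constrained randomisation within each yearly cohort. Enumerate the 3,003 allocations and score their balance. Keep a pre-set best-balanced fraction such as 10%, check that no two classrooms are always or never together, and draw one at random.
3. Balance on two or three variables, mainly focal-child centrality and focal-child DPP.
4. Name these variables in Data Analysis and include them in the Aim 1 and Aim 3 models, and in Aim 2 where the sample size allows.
5. Reconcile the 20:10 and 30:20 counts. The figure of 3,003 applies only to a 10:5 split of 15.

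The cost is a short script and a few protocol sentences. Assignment waits for ratings from all 15 classrooms, and the models must carry the balancing covariates.
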